## 2. OBJECTIVES

Primary Objectives:

- 1) To study PPG signal characteristics in relation to circulatory arrest in patients with induced circulatory arrest.
- 2) To construct a PPG-based algorithm for detection of circulatory arrest based on induced circulatory arrest data in patients.
- 3) To study the performance (sensitivity and false positive alarms) of the developed PPG-based algorithm for detection of circulatory arrest in patients with induced circulatory arrests.

Secondary Objective(s):

- To study the positive predictive value of the developed algorithm for circulatory arrest detection.
- To study the specificity of the developed circulatory arrest detection algorithm.
  
- To identify potential sources of false positive alarms for circulatory arrests.
- To study PPG signal characteristics in relation to hemodynamically stable cardiac arrhythmias.
- To study PPG signal characteristics in relation to hemodynamically unstable cardiac arrhythmias.
- To study PPG signal characteristics prior to and after TAVR procedure to assess the impact of aortic stenosis and/or regurgitation on the PPG signal.
- To study PPG signal characteristics in patients with and without systemic hypertension.
- To study PPG signal characteristics in relation to left ventricular ejection fraction in patients without relevant valvular lesions.

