### 4.4 Sample size calculation

Targeting a desired sensitivity of 95%, 200 true events allow estimation of sensitivity with precision (expressed as expected width of the 95% confidence interval) of +/- 3%, which is considered adequate. As for specificity, a substantially larger number of “non-events” can be sampled, precision for estimating specificity will be larger.

In this study, we will primarily collect data of induced circulatory arrest, obtained during controlled settings with appropriate reference standards (ECG and (invasive) blood pressure measurements). To collect a sufficient amount of PPG data with true events, the

sample size will be 276 patients consisting of an estimated number of n=200 TAVR-patients (event rate 1/1), n=20 ICD-patients (event rate 1/1) and n=56 VT-ablation patients (event rate 1/3). In case ventricular fibrillation induction or rapid ventricular pacing is not performed or does not result in complete circulatory arrest (as determined on (invasive) blood pressure measurements), the number of patients included will be increased to guarantee the anticipated number of true events, with a maximum of 80 additional patients. Data of the patients without induced circulatory arrest will be used as non-cardiac arrest data.

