### **8.3.2 TAVR-patients**

During transcatheter aortic valve replacement (TAVR), rapid ventricular pacing is routinely performed during valve deployment resulting in short-lasting cardiac standstill and circulatory compromise. The wristband is applied prior to the procedure. This enables collection of PPG data during the entire procedure, thus including settings with and without circulatory arrest. Presence of circulatory arrest will be ensured based on simultaneous ECG recordings and invasive pressure data. For the latter, routinely recorded invasive pressure recordings will be used. This data will be digitally stored and collected. During a TAVR, an arterial line is routinely inserted to monitor blood pressure (no study-related intervention). Echocardiographic data pre and post TAVR will also be collected. The wristband is removed after the procedure. Activities are described in Table 1.

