### 8.3.2 VT ablation

During VT ablation, hemodynamically unstable VT/VF is induced in about 1/3 of patients. Patients will wear the wristband during the entire procedure. This enables collection of PPG data in settings with and without circulatory arrest. In case an arterial line is not inserted for clinical purposes, patients will be asked consent to do so. The presence of circulatory arrest is confirmed by simultaneously recorded invasive blood pressure measurements and ECG recordings. Therefore, in patients in whom this is not standard of care, consent will be asked to insert an arterial line into the radial artery to measure blood pressure during ventricular fibrillation to confirm complete circulatory arrest. ECG and invasive blood pressure measurements will be digitally stored and collected. Available echocardiographic data will be collected. The wristband is removed after the procedure. Activities are described in Table 1.

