## 10. STATISTICAL ANALYSIS

Categorical data will be presented as numbers (percentages) and compared using Chi-square test or Fisher's exact test. Continuous data will be assessed for normal distribution and presented as means  $\pm$  standard deviations or medians (interquartile ranges) whichever appropriate. Comparisons will be performed using the Student's t-test or Mann-Whitney U test, whichever appropriate.

For each patient studied, circulatory arrest data (case data) and non-circulatory arrest data (control data) will be collected. The data obtained will be analysed and used for algorithm development at regular intervals: after inclusion of the first 50 patients with at least one circulatory arrest and afterwards after inclusions of another 50 patients. This enables improvement and refinement of the initial algorithm to gain optimal performance. The first iteration provides a first version of the diagnostic algorithm. The second and third iteration will be used to optimize the algorithm. The fourth iteration will be used as final evaluation of the performance of the algorithm (internal validation). All non-circulatory arrest data will be analyzed for false positive circulatory arrest alarms.

As the algorithm will primarily be developed and validated on non-physiologic circulatory arrest induction using rapid ventricular pacing with aortic balloon inflation during transcatheter aortic valve implantation, a second (external) validation will be performed on data of patients with induced shockable cardiac arrest (i.e. induction of ventricular fibrillation or tachycardias). This most closely resembles clinical sudden cardiac arrest. The final cohort of 50 inclusions with at least one induced event, consisting only of patients who underwent VT ablation or VF induction after s-ICD implantation, will be used for this analysis.

The performance of the PPG-based algorithm will be assessed by calculating the sensitivity, specificity, and positive predictive value with 95% confidence intervals. The specificity is reported based on 1-minute intervals of pulsatile PPG signal correctly identified as non-circulatory arrest. Reporting will follow the recommendations of the STARD guidelines for studies on diagnostic accuracy. Statistical analyses will be performed using SPSS (IBM, Armonk, USA).

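### Inductions that stop short of complete arrest become ordinary control data, so alarms during them count as plain false alarms; they need a separate, reported category

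*Protocol*

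**What the plan says.** Section 4.4 foresees two ways in which a patient may supply no true event. Either the induction is not carried out, or it "does not result in complete circulatory arrest (as determined on (invasive) blood pressure measurements"). Up to 80 extra patients may be recruited to make good the loss. The next sentence fixes what happens to the recordings: "Data of the patients without induced circulatory arrest will be used as non-cardiac arrest data". It makes no exception for the minutes around an induction that was attempted.

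Section 10 divides each patient's recording into case data and control data, feeds the collected data into successive rounds of algorithm development, and adds: "All non-circulatory arrest data will be analyzed for false positive circulatory arrest alarms". False positive alarms stand beside sensitivity as the main endpoint in Section 8.1.1. PPV and specificity are secondary (8.1.2). Specificity alone is restricted to one-minute intervals with a pulsatile signal.

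Elsewhere the protocol recognises a state between normal circulation and arrest. One secondary objective reads "To study PPG signal characteristics in relation to hemodynamically unstable cardiac arrhythmias", and the TAVR procedure is described thus: "rapid ventricular pacing is routinely performed during valve deployment resulting in short-lasting cardiac standstill and circulatory compromise".

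**The concern.** The false-alarm endpoint is most useful if it shows how often the wristband would alarm in someone whose circulation is adequate. An alarm while the ventricle is fibrillating or being paced rapidly, with pressure much reduced but not absent, is a different matter. Under the current wording both land in one count, and a reader of the result could not tell them apart.

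The same labels are available to the development rounds. If near-arrest segments carry the control label there, the algorithm is tuned on examples in which a failing circulation is marked as normal. That is an inference from the two-class scheme; the protocol describes no training method from which its effect could be derived.

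**Working it through.** **1. The plan's own figure.** Section 4.4 says: "Targeting a desired sensitivity of 95%, 200 true events allow estimation of sensitivity with precision". It puts that precision at plus or minus 3 percentage points. The Wald half-width is 1.96 × √(0.95 × 0.05 / 200) = 0.0302, or 3.0 percentage points, so the stated precision reproduces. Expected events from the planned mix are 200 × 1 + 20 × 1 + 56 × 1/3 = 238.7, which exceeds 200. The point here concerns labelling and leaves the sample size untouched.

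**2. One segment followed through the rules.** Take a TAVR patient in whom pacing lowers the pressure without producing complete arrest, and who has no other induced arrest.
- 4.4: not a true event, so the patient belongs to the group just described and the recording is non-arrest data.
- Section 10, classes: not case data, therefore control data.
- Section 10, development: part of the data used.
- Section 10, false alarms: scored, because all non-arrest data are scored.
- PPV: an alarm here joins the denominator as a false positive.
- Specificity: counted only if the signal in that minute is pulsatile.

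**3. Illustration of size: count and PPV.** The protocol gives no number of incomplete inductions and no alarm rate, so the inputs are assumptions: k incomplete inductions, an alarm in 25-90% of them, and 190 of 200 arrests detected. Alarms added = k × (0.25 to 0.90). PPV = 190 / (190 + other false alarms + alarms added).

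| k | Alarms added | PPV, no other false alarms (100% before) | PPV, 10 other false alarms (95.0% before) |
|---|---|---|---|
| 10 | 2.5-9 | 98.7-95.5% | 93.8-90.9% |
| 40 | 10-36 | 95.0-84.1% | 90.5-80.5% |
| 80 | 20-72 | 90.5-72.5% | 86.4-69.9% |

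The value 80 is borrowed from the cap on extra patients. That cap also covers inductions never performed, so it is a marker and not an estimate. The 200 events are the planning total of 4.4. Section 10 bases the final evaluation on a cohort of 50, so the reported numbers would be smaller.

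**4. Relative to a background rate.** Assume 2 hours recorded per patient, 0.05-0.2 background false alarms per hour, 20-80 incomplete inductions and an alarm in 30-60% of them.
- Low end: 20 × 0.3 = 6 alarms on 0.2 × 2 × (276 + 20) = 118.4, or +5%.
- High end: 80 × 0.6 = 48 alarms on 0.05 × 2 × (276 + 80) = 35.6, or +135%.

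A range this wide shows that the size cannot be settled from the protocol.

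**5. Specificity.** With 276 + 80 = 356 patients and an assumed 1 hour each, there are 356 × 60 = 21,360 one-minute intervals. The largest case above, with each alarm costing one interval, gives 72 / 21,360 = 0.34 points. With 2 hours it is 0.17 points. The pulsatile restriction would lower this further.

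**The case against.** Four arguments deserve weight.

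- **The sentence may mean only patients never induced.** The note on Amendment 1 describes TAVR patients who did not need pacing, so this may be the intent. But the current 4.4 names incomplete arrest in the sentence immediately before, and nothing narrows the group afterwards. If the narrow meaning is intended, the text should say so.
- **A segment that the reference standard calls non-arrest is rightly a negative.** This is ordinary diagnostic-accuracy practice and it stands. Simply removing these segments would take the hardest negatives out of a co-primary measure and flatter the device. The remedy must therefore show the results both ways.
- **Segment labelling can wait for the SAP, and sources of false alarms are already a secondary endpoint.** A pressure threshold for complete arrest may well be in the SAP, and its absence is not criticised. The criticism is of a rule that 4.4 does state. Listing alarm sources afterwards helps, but it does not separate the main count.
- **Event labels do not differ between procedures.** A reader might infer that the same low-output state is an event in VT ablation but a control in TAVR, because 4.4 plans on an event rate of 1/3 and the VT ablation section says "During VT ablation, hemodynamically unstable VT/VF is induced in about 1/3 of patients". The documents do not support this. That section also requires confirmation by invasive pressure and ECG. The 1/3 is a planning rate, not a case definition. Even with no VT-ablation events, 200 + 20 = 220 planned events exceed 200.

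**Conclusion.** The point holds as one of labelling. Taken literally, 4.4 and Section 10 together place alarms during incomplete inductions in the co-primary false-alarm count and in PPV as ordinary false alarms, and offer those segments to development as plain controls. The effect on the count may be small or substantial. It depends on the number of incomplete inductions and how often the algorithm alarms in them, and the protocol gives neither.

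Two stronger readings are tempting and should not be adopted. Material damage to specificity does not follow: the measure is confined to pulsatile intervals, and under the assumptions above it moves by a third of a point at most. Nor can it be said that the algorithm will become less sensitive, since no training method or threshold rule is given. This is a cheap improvement, not a condition for the study's validity.

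**What to change.** Replace the last sentence of 4.4 and mirror the change in Section 10, along these lines:

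- Patients in whom no induction was performed contribute non-arrest data.
- Where an induction was performed but complete arrest was not reached, the segment from its start until pressure has recovered is labelled incomplete arrest. The rest of the recording is control data.
- Incomplete-arrest segments are not used as plain control data in development.
- The number of these segments and the proportion with an alarm are reported on their own line.
- The false-alarm count and PPV are given twice: with these segments counted as non-arrest, and without them.

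Add to 4.4 that the VT-ablation rate of 1/3 is a planning figure for unstable VT/VF, and so an upper bound for confirmed complete arrests.

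The cost is a few sentences, one extra table row, and relabelling of any incomplete inductions already processed. No information is lost, because both versions of the count are shown. The change should be made before the labels for the final evaluation are locked.

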**5. TREATMENT OF SUBJECTS**

Not applicable.

## **6. INVESTIGATIONAL PRODUCT**

Not applicable.

## 7. NON-INVESTIGATIONAL PRODUCT

### 7.1 Name and description of non-investigational product(s)

PPG data will be collected during hospital stay using the CardioWatch 287-2 (Corsano Health B.V.). The CardioWatch 287 is a medically certified wireless remote monitoring system intended for continuous collection of physiological data in home and healthcare settings. This includes heart rate, heart rate variability (R-R interval), respiration rate, activity and sleep. CardioWatch 287-1 is a CE medical device certified under EU-MDR standards. Additional documentation including certificates and the investigational medical device dossier (IMDD) is available as Attachments. The CardioWatch 287-2 incorporates additional light emitting diodes ((LED); red and infrared light) to improve PPG registration. Data is transmitted wirelessly from the device via the application to a health cloud where it is stored and made available for further analysis. The software complies with the General Data Protection Regulation (GDPR) and Health Insurance Portability and Accountability Act (HIPAA) privacy and security rules.

### 7.2 Summary of findings from non-clinical studies

Summary of information regarding the quality, manufacture and control of the non-investigational medical product can be found in the Investigational Medical Device Dossier (IMDD).

### 7.3 Summary of findings from clinical studies

Summary of information regarding the results of clinical studies of the non-investigational medical product can be found in the Investigational Medical Device Dossier (IMDD).

## **8. METHODS**

### **8.1 Study parameters/endpoints**

#### **8.1.1 Main study parameter/endpoint**

- Sensitivity of the developed algorithm for circulatory arrest detection and false positive circulatory arrest alarms.

#### **8.1.2 Secondary study parameters/endpoints**

- Specificity of the developed circulatory arrest detection algorithm.
- Positive predictive value of the developed algorithm for circulatory arrest detection
- PPG-derived signal characteristics during circulatory and non-circulatory arrest
- Sources of noise
- Sources of false positive alarms

#### **8.1.3 Other study parameters**

- Demographic data
- Medical history including cardiac history and peripheral artery disease
- Cardiovascular risk factors
- Medication use
- Haemoglobin, thyroid function if available
- Echocardiographic parameters of left and right ventricular and valvular functions
- Invasive cardiac pressure and blood pressure recordings
- Non-invasive blood pressure recordings
- Procedural characteristics

### **8.2 Randomisation, blinding and treatment allocation**

Not applicable.

### **8.3 Study procedures**

Study procedures for the above-described groups of study patients are described below.

### **8.3.1 ICD-patients**

As part of routine practice, after subcutaneous implantable cardioverter defibrillator (ICD) implantation or replacement defibrillation testing is performed to test the ability of the implanted device to sense, detect and terminate ventricular fibrillation appropriately. This involves induction of ventricular fibrillation resulting in short-lasting circulatory arrest. During the entire procedure patients will wear the wristband. This enables collection of PPG data in settings with and without circulatory arrest. The presence of circulatory arrest is confirmed by simultaneously recorded invasive blood pressure measurements and ECG recordings. Therefore, in patients in whom this is not standard of care, consent will be asked to insert an arterial line into the radial artery to measure blood pressure during ventricular fibrillation to confirm complete circulatory arrest. ECG and invasive blood pressure measurements will be digitally stored and collected. Available echocardiographic data will be collected. The wristband is removed after the procedure. Activities are described in Table 1.

### **8.3.2 TAVR-patients**

During transcatheter aortic valve replacement (TAVR), rapid ventricular pacing is routinely performed during valve deployment resulting in short-lasting cardiac standstill and circulatory compromise. The wristband is applied prior to the procedure. This enables collection of PPG data during the entire procedure, thus including settings with and without circulatory arrest. Presence of circulatory arrest will be ensured based on simultaneous ECG recordings and invasive pressure data. For the latter, routinely recorded invasive pressure recordings will be used. This data will be digitally stored and collected. During a TAVR, an arterial line is routinely inserted to monitor blood pressure (no study-related intervention). Echocardiographic data pre and post TAVR will also be collected. The wristband is removed after the procedure. Activities are described in Table 1.

### 8.3.2 VT ablation

During VT ablation, hemodynamically unstable VT/VF is induced in about 1/3 of patients. Patients will wear the wristband during the entire procedure. This enables collection of PPG data in settings with and without circulatory arrest. In case an arterial line is not inserted for clinical purposes, patients will be asked consent to do so. The presence of circulatory arrest is confirmed by simultaneously recorded invasive blood pressure measurements and ECG recordings. Therefore, in patients in whom this is not standard of care, consent will be asked to insert an arterial line into the radial artery to measure blood pressure during ventricular fibrillation to confirm complete circulatory arrest. ECG and invasive blood pressure measurements will be digitally stored and collected. Available echocardiographic data will be collected. The wristband is removed after the procedure. Activities are described in Table 1.

**Table 1: Study activities**

TAVR-patients			
Outpatient clinic/hospital admission	Admission/Day of TAVR	TAVR	Day(s) after TAVR
Screening: Check in- and exclusion criteria	Apply wristband for continuous PPG recording	Continue PPG recording using the wristband.	Collect echocardiographic data
Informed consent if eligible		Save invasive (blood) pressure measurements	
Collect baseline data including available echocardiographic data		Annotate rapid ventricular pacing and save ECG monitoring	
		Remove wristband after the procedure	

ICD-patients/VT ablation patients		
Outpatient clinic/hospital admission	Admission	ICD implantation with defibrillation testing
Screening: Check in- and exclusion criteria	Apply wristband for continuous PPG recording	Continue PPG recording using the wristband

Informed consent if eligible	12-lead ECG	Insert an arterial line in the radial artery (opposite arm to the wristband)
Collect baseline data including available echocardiographic data		Initiate and save (non-)invasive blood pressure measurements
		Annotate defibrillation testing and save ECG monitoring
		Remove arterial line and wristband after the procedure

#### **8.4 Withdrawal of individual subjects**

Subjects can leave the study at any time for any reason if they wish to do so without any consequences. The investigator can decide to withdraw a subject from the study for urgent medical reasons.

##### **8.4.1 Specific criteria for withdrawal (if applicable)**

Not applicable.

#### **8.5 Replacement of individual subjects after withdrawal**

In case of withdrawal, subjects will be replaced to facilitate achievement of the needed number of true events to guarantee useful study results.

#### **8.6 Follow-up of subjects withdrawn from treatment**

No follow-up will be performed.

#### **8.7 Premature termination of the study**

Not applicable.

## 9. SAFETY REPORTING

### 9.1 Temporary halt for reasons of subject safety

In accordance to section 10, subsection 4, of the WMO, the sponsor will suspend the study if there is sufficient ground that continuation of the study will jeopardise subject health or safety. The sponsor will notify the accredited METC without undue delay of a temporary halt including the reason for such an action. The study will be suspended pending a further positive decision by the accredited METC. The investigator will take care that all subjects are kept informed.

### 9.2 AEs, SAEs and SUSARs

#### 9.2.1 Adverse events (AEs)

Adverse events are defined as any undesirable experience occurring to a subject during the study, whether or not considered related to the study. All adverse events reported spontaneously by the subject or observed by the investigator or his staff will be recorded.

Given the observational design of this study, with only additional diagnostic data collection using a PPG sensor in a wristband, the study will follow the recommendations of observational studies with additional diagnostic investigations. Only adverse events related to the use of the wristband or study-related insertion of an arterial line will be documented.

